#### 4.2.9. Visit Windows

All data listings that contain an evaluation date will contain a relative study day (Rel Day Dose 1). Pre-treatment and post-treatment study days are numbered relative to the day of the first dose of study treatment, which is designated as Day 1. The preceding day is Day -1, the day before that is Day -2, etc. Listings will also contain a study day (Rel Day Dose 2) relative to the second dose of study treatment, which is designated as Day 1. For patients that do not receive a second dose, Rel Day Dose 2 will be "NA". For Rel Day Dose 2, preceding days (e.g., Day -1, -2) will not be derived or presented. In other words, if the date is prior to Dose 2, only Rel Day Dose 1 will be presented. If the date is after Dose 2, then both Rel Day Dose 1 and Rel Day Dose 2 will be presented.

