**Unscheduled visit windowing:**

If a patient receives their second dose of study medication at an unscheduled visit that is not  $>3$  weeks after Week 24, the dosing information and all other data collected at that visit will be mapped to the closest nominal visit, based on Rel Day Dose 1, even if data is already available in that visit. All data collected at the time of the second dose will be used for analysis. If data is available in the nominal visit, but was not collected at the unscheduled visit associated with the second dose, the data from the nominal visit will be used. If a patient receives their second dose at an unscheduled visit that is  $> 3$  weeks past Week 24, data from that unscheduled visit will not be used for time to second dose analyses or exploratory efficacy analyses involving two-dose patients.

Data collected at unscheduled visits that are not associated with the second dose will be mapped to the closest scheduled visit, but only if that data is not already available in that visit. Otherwise data will be summarized and presented according to the nominal visit as recorded on the Case Report Form (CRF).

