**4.2.10.      Baseline Definitions**

Baseline for the first dose is the baseline/Day 1 assessment prior to administration of the first dose of study treatment. If the baseline result is missing, the last non-missing result prior to administration of study treatment may be used from the Screening period.

Baseline for the second dose of study treatment is defined as the last data collected prior to the second dose of study treatment administration. This is the same study visit, as long as the data are collected prior to the second dose.

Where noted in this SAP, change from baseline for efficacy analyses are also performed where baseline for the second dose is defined as the baseline/Day 1 assessment prior to administration of the first dose of study treatment.

Additional baselines may be defined to explore efficacy endpoints comparing the first dose and the second dose of study treatment administration. All new baseline definitions will be fully specified and documented in an interim SAP (iSAP) and in the final CSR.

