#### 4.9.1.2. Change from baseline, patients receiving two doses

##### Change from Baseline to Week 12

A within patient analysis will be completed for patients who receive two doses of FX006. Change in WOMAC A, WOMAC B, WOMAC C and WOMAC total from first dose (Day 1) to Week 12 will be compared to change in WOMAC from second dose to 12 weeks after the second dose using a paired t-test.

The paired t-test will be completed by using the SAS/STAT® PROC MIXED procedure. Using the PROC MIXED procedure allows for multivariate modelling. Model covariates are study site, baseline WOMAC score, and potentially other covariates. Baseline WOMAC score for the first dose comes from the baseline visit. Baseline WOMAC score for the second dose comes from the second dose visit.

Descriptive statistics will include number of observations, unadjusted mean, standard deviation, median, minimum and maximum. Change from baseline LSM, SE and 95% CI from the mixed model will also be presented. The difference between the first dose (the control) and the second dose will be presented, and estimated via LSM from the analysis model along with 95% confidence intervals and associated 2-sided p-values. This model assumes that missing values are missing at random. Only patients that have data for both time points (i.e., change from Day 1 to Week 12 and change from the second dose to 12 weeks after the second dose) will be included in the model.

All patients who receive two doses of FX006 will be combined in the analysis and results will be displayed in the same table.

Sample SAS code that can be used to implement the analysis is provided below:

```
proc mixed data=<ADaM> method=type3;
  class subjID site arm;
  model chg = base site arm/ alpha=0.05 ddfm=kr outp=pred residual solution;
  random subjID;
  lsmeans arm / diff cl alpha=0.05;
  ods output diff=diff1 lsmeans=lsml;
run;
quit;
```

In the above code, "arm" refers to the first or second dose administered (coded as a 1 or 2).

The analysis above will also be performed to compare the changes in WOMAC A, WOMAC B, WOMAC C and WOMAC total from first dose (Day 1) to Week 12 to the changes from first dose (Day 1) to 12 weeks after the second dose.

#### Change from Baseline to Week 4, 8 and 12

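### SAP 4.2.9 fills gaps at an off-schedule second-dose visit from the closest nominal visit without requiring pre-injection data, so post-dose WOMAC or KOOS values can stand as that visit's values

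*SAP*

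**What the plan says.** SAP 4.2.9, unscheduled visit windowing, covers second doses given at an unscheduled visit up to 3 weeks after Week 24. It has three steps:

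- The dosing visit is "mapped to the closest nominal visit, based on Rel Day Dose 1, even if data is already available in that visit".
- Data from the dosing visit come first: "All data collected at the time of the second dose will be used for analysis".
- Gaps are filled from the nominal visit: where an item was "not collected at the unscheduled visit associated with the second dose, the data from the nominal visit will be used".

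None of the steps says whether the nominal visit must come before the injection.

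SAP 4.2.10 then defines the second-dose baseline: "Baseline for the second dose of study treatment is defined as the last data collected prior to the second dose of study treatment administration". It adds: "This is the same study visit, as long as the data are collected prior to the second dose". The endpoint text in SAP 4.9.1.2 is looser: "Baseline WOMAC score for the second dose comes from the second dose visit". SAP 4.9.1.4 repeats that statement for both AUE comparisons. Neither section repeats the pre-dose condition or refers to 4.2.10.

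The date information needed to tell the two cases apart already exists, since 4.2.9 derives a day count relative to each dose: "If the date is after Dose 2, then both Rel Day Dose 1 and Rel Day Dose 2 will be presented".

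**The concern.** Mapping to the closest visit works in both directions. If a patient is dosed between two scheduled visits and nearer the later one, the mapped visit takes place after the injection. Read literally, the back-fill rule then puts a treated score into the slot that is labelled as the second-dose visit.

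Two things are at stake.

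1. **Results keyed to the visit label.** The by-visit WOMAC summaries (4.9.1.1), the KOOS summaries built the same way (4.9.2) and the WOMAC A responder rates (4.9.1.3) would carry the value as that visit's result. The first-dose AUE in Table 3 ends at the second-dose visit, so second-dose relief would be counted as durability of the first dose. Section 4.2.10 does not protect these, because it governs only the baseline.
2. **The second-dose baseline.** A programmer who follows 4.2.10 takes the last pre-dose value. One who follows 4.9.1.2 or 4.9.1.4 literally, after the 4.2.9 mapping, may take the post-dose value. The SAP does not say which wording prevails.

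Both errors would make the second dose look weaker relative to the first.

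**Working it through.** The plan gives no figure on this point, so there is none to reproduce. The check lists the possible dosing days and then traces where a back-filled value goes.

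**Inputs.** Visits are 4 weeks apart (Protocol 7.1). The second dose is possible from Week 12, and the mapping applies up to 3 weeks after Week 24 (SAP 4.2.9). The visit tolerance is ±7 days (Protocol Table 1, footnote 2). Assumption: scheduled day = 7 × week + 1, so Weeks 12, 16, 20, 24 and 28 fall on Days 85, 113, 141, 169 and 197. Using 7 × week instead gives the same counts.

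**Off-schedule days.** Day 86 to Day 169 + 21 = 190 is 105 days. Removing the three scheduled days (113, 141, 169) leaves 102.

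| Span | Closest visit before dose | Tie | Closest visit after dose |
|---|---|---|---|
| Week 12–16, 16–20, 20–24 (27 days each) | 3 × 13 = 39 | 3 | 3 × 13 = 39 |
| 1–21 days after Week 24 | 13 | 1 | 7 |
| Total | 52 | 4 | 46 |

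The SAP gives no rule for ties. On the last 7 days (15–21 days after Week 24) the closest visit is Week 28, which has no column in 4.9.1.1 or Table 3.

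The ±7-day tolerance adds the days on which the closest scheduled day is 1 to 6 days before the dose but the visit itself could be held after it. That is 4 × 6 = 24 days, giving 46 + 24 = 70 of 102.

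**Example.** A second dose on Day 104 is 104 − 85 = 19 days after Week 12 and 113 − 104 = 9 days before Week 16, so it maps to Week 16. If no WOMAC was taken on Day 104, the Week 16 slot takes the Day 113 score, 9 days after the injection. Across the 46 days this gap is 1 to 13 days. Protocol 5.2.7.1 reports median onset of pain relief at 1 to 2 days, so such a score is likely to reflect the second dose.

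**Where the value goes.** With the trapezoidal rule in 4.9.1.4 and 4-week steps, the first-dose AUE for this patient (Week 4 to Week 16) is

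2·WD4 + 4·WD8 + 4·WD12 + 2·WD16.

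If the second dose lowers the Week 16 score by d points, the first-dose AUE shifts by 2d score-weeks towards more relief. The end value carries 2/12 = 1/6 of the weight when the second dose maps to Week 16, 2/16 = 1/8 at Week 20 and 2/20 = 1/10 at Week 24. If a fraction f of the patients in a column is affected, the column mean shifts by 2·f·d. The documents give neither f nor d.

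At nominal timing the separate Week 4 to Week 12 AUE scores are not affected, because no dose in this range maps to an earlier-than-dose slot at Week 12 that is filled after the injection.

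**Baseline for the same patient.** Section 4.2.10 selects the last WOMAC before Day 104, normally Week 12. Section 4.9.1.2, read on the mapped visit, selects Day 113. The two differ.

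**The case against.** The strongest answer is that 4.2.10 is the SAP's definition of baseline, and its same-visit sentence is an explicit guard. On this view the endpoint sections use second-dose visit only as shorthand to distinguish the two baselines and do not replace the definition. This largely stands. A reader might infer that the plan makes a post-injection score the second-dose baseline. The documents do not support that: 4.2.10 excludes it, and it arises only if the looser wording is programmed instead. What remains is a conflict of wording.

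A second answer is that 4.2.9 is silent on order, and that a natural case is evaluation at a nominal visit followed by a later injection, where back-fill uses pre-dose data. That is plausible, but the rule as written covers both directions.

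A reader might also infer that the second-dose-visit rows for laboratory values, vital signs and knee assessment would hold post-injection data. Protocol Table 1, footnote 6, schedules these items in Weeks 12–24 only before a second dose, or at the final visit of patients not eligible for one. After an off-schedule injection the next nominal visit would normally have none to back-fill, so that harm largely falls away.

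Finally, exposure is limited. A case needs an off-schedule dose, a later closest visit and a questionnaire missing at dosing. WOMAC A is part of the repeat-dose criteria (Protocol 7.4.3.1), although a clinical rationale can replace the score threshold. The paired comparison in 4.9.1.2 is also run from the Day 1 baseline, which avoids the baseline conflict in the change scores. These points stand and keep the severity low.

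**Conclusion.** The gap is real but small. SAP 4.2.9, followed literally, can place a post-injection WOMAC or KOOS value in the second-dose visit slot. From there it reaches by-visit summaries and, for WOMAC, responder rates and the end of the first-dose AUE interval in Table 3. Separately, 4.2.10 and the endpoint sections can select different second-dose baselines for the same patient.

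The only size that can be given is 46 of 102 possible off-schedule days at nominal timing, or up to 70 with the visit tolerance. These counts assume scheduled days at 7 × week + 1 and mapping by scheduled day. They are not patient frequencies and should not be read as saying that about half of off-schedule patients are affected. The number affected is unknown and probably small. The consequences are confined to exploratory efficacy.

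**What to change.** 1. In SAP 4.2.9, allow back-fill only from nominal-visit data collected before the second-dose date and time. State that later values are never used as second-dose-visit values or in first-dose intervals.
2. If the mapped visit has no pre-dose value, leave that visit's value missing for by-visit and AUE use, and take the second-dose baseline from 4.2.10 (the last value before the second dose). Under 4.9.1.4 the final 4-week interval then drops out of the first-dose sum, so the SAP should also say how the paired AUE comparison handles the shorter interval.
3. In 4.9.1.2 and 4.9.1.4, replace the statement that the second-dose baseline comes from the second-dose visit with a reference to 4.2.10.

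Values taken soon after the injection need not be moved to a post-second-dose time point. A score from day 9, for example, is not a 4-week result, and it can stay in the listings under its own date.

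The cost is a few sentences in the SAP and a date check in the analysis datasets. No new data are needed.

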**4.2.10.      Baseline Definitions**

Baseline for the first dose is the baseline/Day 1 assessment prior to administration of the first dose of study treatment. If the baseline result is missing, the last non-missing result prior to administration of study treatment may be used from the Screening period.

Baseline for the second dose of study treatment is defined as the last data collected prior to the second dose of study treatment administration. This is the same study visit, as long as the data are collected prior to the second dose.

Where noted in this SAP, change from baseline for efficacy analyses are also performed where baseline for the second dose is defined as the baseline/Day 1 assessment prior to administration of the first dose of study treatment.

Additional baselines may be defined to explore efficacy endpoints comparing the first dose and the second dose of study treatment administration. All new baseline definitions will be fully specified and documented in an interim SAP (iSAP) and in the final CSR.

#### **4.3. Interim Analyses**

Interim analyses may be conducted evaluating safety and efficacy signals following administration of one or two doses of 32mg FX006. These interim analyses on exploratory endpoints may be completed for data review, regulatory updates, and/or publication (or presentation at congresses) for this open-label study. For any analyses completed not presently identified in this SAP an iSAP will be written and approved prior to interim analysis.. The iSAP will describe the purpose and analytical objectives of the interim analysis. Any changes made to the final analysis will be documented in an amendment to the SAP prior to final analysis. Final analyses will be conducted after completion of the study, when all patients have either discontinued the study early (prior to Week 52) or completed the study through Week 52.

#### **4.4. Final Analysis**

All final analyses will be completed following database lock. Final analyses specified in the protocol and SAP will be completed and reported in the CSR. Interim analyses conducted with exploratory endpoints to examine efficacy signals prior to database lock will also be reported in the final CSR. Post-hoc, or additional exploratory analyses, not defined in the SAP may be completed to further understanding and elucidation of the study results. Any post-hoc, exploratory, analyses completed will be clearly identified as such in the final CSR.

#### **4.5. Patient Disposition**

All patients who are enrolled will be accounted for in this study.

Patient disposition will be tabulated and include the total number of patients enrolled, treated, completed and early terminated, reason for early termination and the number in each patient population for analysis.

Subject completion will be presented overall and by the following categories:

1. At Week 12 (no clinical benefit)
2. At Week 24 (not clinically indicated to receive second injection)
3. At Week 52

Early termination will be presented overall and by the following time periods:

1. Prior to Week 12, which is the first visit for second dose eligibility
2. On or after Week 12, but prior to receiving second dose
3. On or after second dose and prior to 12 Weeks after second dose
4. On or after receiving the second dose but prior to Week 52

The following by-patient data listings will be presented:

- Study completion information including the reason for premature study discontinuation, if applicable.
- Inclusion/exclusion criteria not met.
- Repeat dose inclusion/exclusion criteria not met for all patients. If a patient receives a repeat dose on a visit where repeat dose inclusion/exclusion criteria were not met, that visit will be flagged.
- Repeat dose eligibility at Weeks 12, 16, 20 and 24.
- Patient inclusion in each of the analysis populations (SP, FAS, BP and PPIP). Reasons for exclusion from the PPIP will be presented.

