## 7. INVESTIGATIONAL PLAN

### 7.1. Overall Study Design and Plan

This study is an open-label, repeat administration design of 32 mg FX006. The study will be conducted in male and female patients  $\geq$  40 years of age with symptomatic OA of the knee.

Eligible patients will be offered participation to receive an initial IA injection of FX006 administered to the index knee at Day 1

Patients who receive an initial injection of FX006 will return at Weeks 4 and 8 before being evaluated at 12, 16, 20, and 24 weeks following the initial administration of FX006 for repeat administration. At the first visit where the patient has been determined to meet repeat administration eligibility criteria described in Section 7.4.3, the patient will be eligible to receive a second IA injection of FX006 administered to the index knee.

Patients who are eligible to receive a second injection will be evaluated for a total of 52 weeks post initial injection at: Weeks 4, 8, 12, 16, 20, 24, 28, 32, 36, 40, 44, 48, and 52, regardless of the visit at which they receive their second injection.

Patients that do not benefit from the initial treatment as determined by evaluation at Week 12 will complete the study at the Week 12 follow-up visit. These patients will be evaluated for a total of 12 weeks post initial injection at: Weeks 4, 8, 12.

Patients who are not eligible for a second injection of FX006 after evaluation at Weeks 12, 16, 20, and 24 will complete the study at the Week 24 follow-up visit. These patients will be evaluated for a total of 24 weeks post initial injection at: Weeks 4, 8, 12, 16, 20, and 24.

Refer to [Appendix 2 Study Visit Flow Chart](#).

The study is expected to enroll over approximately 6 months.

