##### **7.4.3.1. Repeat Administration Inclusion Criteria**

To be eligible to receive a repeat administration, patients must fulfill the following criteria:

1. Benefit from the initial dose of FX006 in the opinion of both the patient and the Investigator
2. No major safety concerns during the initial dose period as assessed by the Investigator
3. Clinically indicated to receive a second dose of FX006 in the opinion of both the patient and the Investigator
4. WOMAC A total sum score of  $\geq 6$  or a clinical rationale as to why a second dose is indicated
5. Compliant with study procedures and visit schedules through at least Week 12 and the willingness and ability to continue to comply through Week 52
6. Willingness to abstain from use of protocol-restricted medications during the study

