#### **4.2.7. Discontinuations and Loss to Follow-up**

Each treated patient in this study will receive an initial injection of FX006 and then be reevaluated starting at Week 12 for eligibility to receive a second injection. Therefore, discontinuation from treatment is not applicable. Whether or not patients receive the entire contents of study drug injection will be considered in the study drug exposure analyses.

Each patient may discontinue from the study for further assessments and study visits. Data collected from discontinued patients will be included in the CSR. Patients who discontinue from the study may be replaced at the discretion of the sponsor.

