#### **4.8. Study Drug Exposure**

Details of study drug administration will be tabulated and presented for the SP by the following groups:

- First (and only) dose for patients receiving one dose
- First dose for patients receiving two doses
- Second dose for patients receiving two doses

The position of knee during injection, approach during injection, whether or not the entire contents of the syringe was injected, reason (if entire contents not injected), the numbing agent used, whether or not ultrasound guidance was used, volume of synovial fluid aspirated, and whether a 20 or 21-gauge needle was used will be presented.

Benefit from the initial dose of FX006 and patients with no major safety concerns during the initial dose period will be summarized for the Week 12 visit. In addition, patients clinically indicated to receive a second dose of FX006 and patients eligible for the second dose at Weeks 12, 16, 20 and 24 will be summarized, as well as the number of patients receiving the second dose at each of these visits. These data come from the “Repeat Dose Eligibility” CRF.

Patients receiving one dose and two doses and the visit at which the second dose was received will be summarized.

A summary of time to second dose will be displayed for patients receiving two doses. The median time to second dose will be estimated based on the 50th percentile of the Kaplan-Meier distribution. Additional summary statistics will be presented, including the 25th and 75th percentiles, and the corresponding 95% confidence intervals.

Additionally, repeat dose data will be presented separately by the following subgroups:

- K-L Grade 2, 3 and 4

- Prior IA steroid injection
- Unilateral/bilateral knee OA
- Prior index knee OA surgery or procedure

All study drug exposure data will be presented in a data listing.

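### SAP 4.5 labels every Week 24 completer as not clinically indicated, and no summary table counts patients denied the second dose on a safety criterion

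*SAP*

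**What the plan says.** **Exits from the study.** Protocol 7.1, repeated in SAP 2.1, gives three planned end points. Patients without benefit at Week 12 finish there. Patients who receive a second injection are followed to Week 52. For the rest, "Patients who are not eligible for a second injection of FX006 after evaluation at Weeks 12, 16, 20, and 24 will complete the study" at Week 24. That last route is defined by ineligibility alone, with no reason named.

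**Criteria for the second dose.** Protocol 7.4.3.1 keeps safety and indication apart. Inclusion 2 is "No major safety concerns during the initial dose period as assessed by the Investigator"; inclusion 3 is "Clinically indicated to receive a second dose of FX006 in the opinion of both the patient and the Investigator". Protocol 7.4.3.2 adds exclusions, several of them safety-related: active knee infection or crystal disease, allergic reaction to the first dose, recent infection needing antibiotics, broken skin at the injection site, and other medical conditions that in the investigator's judgement stand against the injection.

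**Disposition.** SAP 4.5 tabulates completion as "At Week 12 (no clinical benefit", "At Week 24 (not clinically indicated to receive second injection", or at Week 52. Early terminations are tabulated separately, with reason and period. Repeat-dose criteria not met appear in a by-patient listing.

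**Exposure.** Under SAP 4.8, "patients with no major safety concerns during the initial dose period will be summarized for the Week 12 visit". Indication and eligibility are summarised at Weeks 12, 16, 20 and 24.

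**Adverse events.** SAP 4.10.1 has rows for TEAEs leading to study discontinuation and none for TEAEs leading to no second dose. SAP 4.2.7 describes one injection followed by an eligibility evaluation and concludes: "Therefore, discontinuation from treatment is not applicable".

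**The concern.** The primary objective is the safety and tolerability of repeat administration. A reader of the study report will want to know how many treated patients could not go on to a second injection for safety reasons, and a count of zero would also be informative. As planned, the disposition table would place such a patient among those who did not need the injection, and no other summary table would correct that impression. The two-dose tables cannot supply the number, because they contain only patients who passed the safety criteria.

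**Working it through.** **Step 1: map each route to a single dose onto the SAP 4.5 categories.**

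| Route | Exit | SAP 4.5 category | Reason shown correctly? |
|---|---|---|---|
| No benefit at Week 12 | Completes Week 12 | No clinical benefit | Yes for benefit; any safety bar as well is not shown here |
| Benefited, not indicated through Week 24 | Completes Week 24 | Not clinically indicated | Yes |
| Benefited, barred on a safety criterion through Week 24, stays in study | Completes Week 24 | Not clinically indicated | No |
| Benefited, barred on another criterion (e.g. vaccine, restricted agent, non-compliance) | Completes Week 24 | Not clinically indicated | No |
| Leaves before the second dose | Early termination | Reason and period tabulated | Yes |

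The third and fourth routes have no correct category. The SAP can also disagree with itself: a patient in the third route may count as indicated but not eligible in SAP 4.8, and as not indicated in SAP 4.5.

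**Step 2: look for the third route in every other planned summary.**

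- SAP 4.8, safety item: Week 12 only, although eligibility is assessed to Week 24.
- SAP 4.8, indicated and eligible at four visits: eligibility requires indication, so indicated minus eligible gives patients who were indicated but failed some other criterion. The difference mixes safety bars with vaccines, restricted drugs and non-compliance.
- SAP 4.10.1, TEAEs leading to study discontinuation: a patient who stays to Week 24 has not discontinued.
- SAP 4.10.1, one-dose tables (first dose to Week 12 and to Week 24): the event is included, with seriousness, severity and relationship, but nothing ties it to the withheld dose.
- SAP 4.10.1, two-dose tables: the patient is not in them.
- SAP 4.5, listing of criteria not met: the patient is there, but not counted.

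So the events are tabulated, and the number of patients denied a second dose for safety is not.

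**Step 3: size.** The plan's own figures (Protocol 9.3, SAP 4.1) are 200 enrolled, 66% eligible for a second dose and 75% of those completing.

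- 200 × 0.66 × 0.75 = 99.0, against the stated 100.
- 100 / (0.66 × 0.75) = 202.0, against the stated 200 or so. The figures reproduce.
- One-dose patients expected at design: 200 − 200 × 0.66 = 200 − 132 = 68.

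SAP 5 reports about 10 one-dose patients and more than 90% with two doses. All five routes share those 10, so the safety-barred number x lies between 0 and about 10. The number treated, N, is not given. The SAP 5 figures imply 10/N < 0.10, so N > 100. The share is x/N:

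| Assumed N | x = 0 | x = 1 | x = 10 |
|---|---|---|---|
| 110 | 0% | 0.9% | 9.1% |
| 150 | 0% | 0.7% | 6.7% |
| 200 | 0% | 0.5% | 5.0% |
| 220 | 0% | 0.5% | 4.5% |

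At N = 200 the exact (Clopper-Pearson) 95% interval is 0 to 1.8% for x = 0, and 2.4% to 9.0% for x = 10.

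**The case against.** The strongest reply is that these patients are already visible. The Safety Population is everyone treated, and one-dose patients have their own TEAE tables to Week 24. With about 10 people in that group, any event behind a missed dose is easy to find, including one that starts after Week 12. A patient whom the investigator withdraws is an early termination with a tabulated reason. This stands. It rules out the inference that the adverse events are lost, or that a late safety concern leaves no trace in any table.

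It is also fair to say that the SAP never states where a safety-barred completer goes. The placement follows from reading Protocol 7.1 with the three labels in SAP 4.5. But those labels offer no other place for a patient who benefited and stayed to Week 24.

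A third reply is that some bars, such as recent antibiotics or broken skin, need not be drug-related and may only postpone dosing, since patients are re-evaluated every four weeks. This also stands, and any count should be limited to patients who never received the second dose.

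Finally, a reader might infer that SAP 4.2.7 is wrong and that a withheld second dose should be called treatment discontinuation. The documents do not require that. The second injection is conditional, and SAP 4.2.7 explains its position.

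**Conclusion.** The point holds as a reporting gap. Followed as written, SAP 4.5 misclassifies a safety-barred completer, and no summary table gives the number denied a second dose for safety. What is missing is the count and the link from event to withheld dose.

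At most about 10 patients are affected: 0% to 5% if 200 were treated, and up to 9.1% if only 110 were. N is an assumption, and the documents do not say how the 10 divide among the routes, so zero is possible.

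Two stronger readings are not supported. One is that the plan hides the main tolerability failure of repeat dosing. These patients had one dose, so the event limits access to repeat dosing; tolerability after the second dose is covered by the two-dose TEAE tables and by the early-termination periods that follow it. The other is that the omitted rate rivals the 1.9% SAE rate for FX006 in Protocol 5.2.8. That would need an assumed number of safety-barred patients, and the comparison is not like for like: a barred patient need not have had an SAE, and any SAE would be counted in the SAE rows.

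The change is still worth making, because safety is the primary objective and the correction is cheap.

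**What to change.** - **SAP 4.5:** relabel the Week 24 category as not eligible for second injection. Split one-dose completers by reason: no benefit; not indicated; safety criterion; other criterion. State in advance which Protocol 7.4.3 criteria count as safety, and how a patient failing more than one is shown.
- **SAP 4.8:** extend the major-safety-concern summary to Weeks 16, 20 and 24, and tabulate the repeat-dose exclusion criteria not met.
- **SAP 4.10.1:** add a row for TEAEs leading to no second dose, with all treated patients as denominator, counting only patients who never received it.
- **SAP 4.2.7:** no change needed.

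The cost is SAP wording and a few table rows; sample size, visits and clinical rules are untouched. SAP 4.8 shows that benefit, safety concern, indication and eligibility are on the Repeat Dose Eligibility CRF, SAP 4.5 already lists criteria not met, and Protocol 8.1.2 requires action taken for each adverse event. Whether the CRF links a specific event to a withheld dose cannot be seen from the documents; if it does not, the new row needs a documented review of about 10 patients. The downside is a possibly less favourable tolerability figure.
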